1. PURPOSE OF THE STUDY AND BACKGROUND

1.1 Purpose of the study

The goal of this study is to determine if administering the anti-nausea medication ondansetron prior to doxycycline will decrease the rates of nausea and vomiting in patients taking doxycycline for antibiotic prophylaxis prior to undergoing surgical pregnancy termination.

1.2 Background

The use of prophylactic antibiotics are standard of care to prevent surgical site infections in gynecologic surgery¹. Doxycycline is the recommended antibiotic of choice for surgical pregnancy termination and completion of spontaneous abortion given its effectiveness, low cost, and rare occurrence of allergic reaction². Previous studies have shown that a common side effect of doxycycline is nausea and vomiting, with reported rates as high as 30-40%³. Nausea and vomiting may be reduced by taking the antibiotic with food⁴. Doxycycline given on an empty stomach the morning of a surgical pregnancy termination resulted in nausea and vomiting in 50% of patients and this rate was decreased to 15% when it was taken with food the night before surgery⁵. It is not known whether the use of scheduled prophylactic anti-emetics prior to doxycycline use would further reduce the rate of associated nausea and vomiting. The goal of our proposed study is to determine this.

Our study will be a double blinded randomized controlled trial that will examine whether the use of scheduled prophylactic anti-emetics prior to doxycycline use reduces the incidence of associated nausea and vomiting. Nausea and vomiting is distressing to patients and it affects their perioperative care. It is well documented that minor gynecologic procedures, such as uterine evacuations, can be performed safely with moderate and deep sedation without an endotracheal tube⁶. At our institution, patients experiencing nausea and vomiting prior to a surgical procedure receive

general anesthesia with endotracheal intubation, due to their symptoms, not because that would be the preferred route of anesthesia. For minor gynecologic procedures, the time for general anesthesia induction can be as long as the duration of the entire surgical procedure would be without general anesthesia. The use of general anesthesia increases the duration of time in the operating room, which increases the costs of operating room and anesthesia time, as well as recovery time for the patient⁷. General anesthesia also poses possible risks such as impairment of cardiovascular function and development of pneumonia^{8,9}.

In addition to anesthesia risks and patient discomfort, nausea and vomiting may also affect antibiotic efficacy due to reduced serum levels. Reeves' et al. showed lower serum doxycycline levels in patients with emesis within one hour of doxycycline administration. A serum level greater than 0.8 mg/L has been shown to provide adequate antibiotic prophylaxis. Vomiting after ingestion of doxycycline decreased serum levels by an average of 0.26 mg/L⁵.

Reducing the rates of nausea and vomiting in patients undergoing minor gynecologic procedures may increase the efficacy of antibiotic prophylaxis, and decrease the rates of general anesthesia, patient risks and hospital costs. Most importantly, decreased nausea and vomiting will certainly improve patient experience and is clinically relevant because doxycycline is an antibiotic commonly used for many gynecologic procedures.

2. STUDY DESIGN

2.1 Overview

This will be a randomized controlled trial. Data will be collected by asking patients to fill out a demographic questionnaire and a baseline visual analog scale rating their nausea, pain and anxiety at their clinic appointment 1-2 days prior to their procedure. Patients will then take either ondansetron or a placebo 30 minutes prior to taking doxycycline the night before their procedure. They will then fill out a symptom/medication log recording their symptoms from the time that they take the study medication to the time that they present for their procedure. When they present for their procedure, patients will fill out a second identical visual analog scale rating nausea, pain and anxiety. The primary outcome is nausea and vomiting after taking the study drug and doxycycline the night prior to surgery. Doxycycline prophylaxis the night prior to surgery is the current standard of care. Eligible patients will be enrolled over the course of two years.

2.2 Rationale for Study Design

A randomized controlled trial was selected in order to study ondansetron's effect on the rates of nausea and vomiting in our particular population, so that patients will not know if they are being given ondansetron or placebo before taking doxycycline. Some potential barriers that are expected in the study include that the patients may not fill out their symptom/medication log as this will be done at home. There are approximately 450 patients undergoing surgical termination of pregnancy at the

University of Rochester each year. In order to attain our goal sample size of 300 patients, we would have to enroll a large portion of the total patients. The primary hypothesis is that the rate of nausea and vomiting in patients undergoing surgical pregnancy termination will be decreased in the group receiving ondansetron versus the group receiving placebo.

3. CHARACTERISTICS OF THE RESEARCH POPULATION

3.1 Subject Characteristics

- 3.1.1 **Number of Subjects:** 320 total subjects are expected to participate in the study. 160 total subjects will be randomized to receive ondansetron, while 160 total subjects will be randomized to receive placebo.
- 3.1.2 **Gender and Age of Subjects:** Patients included in the study will be pregnant females that are ages 18-45 years old.
- 3.1.3 **Racial and Ethnic Origin:** There will be no racial or ethnic restrictions to participation.
- 3.1.4 **Vulnerable Subjects:** The women included in this study will be pregnant, although the study interventions are surveys and the administration of a medication that is both safe in pregnancy and commonly used in pregnancy, ondansetron.

3.2 Inclusion and Exclusion Criteria

- 3.2.1 **Inclusion Criteria:**
 - Pregnant women seeking care at the University of Rochester's Women's Health Practice Family Planning Clinic
 - Ages 18-45 years old
 - Undergoing second trimester surgical termination of pregnancy
 - Proficient in reading, writing, and comprehending English
 - Able to give informed consent
- 3.2.2 **Exclusion Criteria:**
 - Less than 18 years old or older than 45 years old
 - Not proficient in reading, writing, or comprehending English
 - Not able to give informed consent
 - Already taking antiemetics
 - Doxycycline allergy
 - Hyperemesis gravidarum
 - History of gastroparesis or cyclical vomiting
 - Unable to swallow pills

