3.3 Discussion of Subject Population

Pregnant women ages 18-45 years old were selected for this study, as they will already be taking doxycycline as the standard of care when they present for abortion care.

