4.2 Process of Consent

Patients will be consented by either [name], [name], the study coordinator, [name], [name], [name], [name] or medical student [name]. The patients will be given a written consent form to sign that will be extensively reviewed with the individual consenting them. The written consents will be stored in a locked filing cabinet, and only the study coordinator, [name] or [name] will be able to access them.

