5. METHODS AND STUDY PROCEDURES

Patients will be approached for participation in the randomized controlled trial after they have completed their pre-operative consultation and have already consented for pregnancy termination. Once patients are consented, they will be randomized to either the placebo or ondansetron group. The study medication will be taken 30 minutes prior to doxycycline medication the night prior to the pregnancy termination. Doxycycline prophylaxis is currently the standard of care, and is not part of the study procedure. Randomization scheme will be generated by computer generated random number blocks using a 1:1 ratio. Allocation will be done by sequentially numbered opaque sealed envelopes. The pharmacy will be compounding the study medication so that it looks exactly like the placebo tablet, in appearance, texture and smell. Once consented and randomized during their clinic visit 1-2 days before the procedure, patients will fill out a demographic questionnaire regarding their age, race, relationship status, income and education level, pregnancy history, gestational age, and symptoms of nausea and vomiting thus far in the pregnancy. This questionnaire will also include questions regarding cigarette and THC use, as well as any diagnoses of gastroesophageal reflux disease or hyperemesis gravidarum. They will then fill out a baseline visual analog scale rating their nausea, pain and anxiety, prior to leaving the office.

The study coordinator will also conduct a chart review for select information. For participants enrolled prior to this version date, it will be retrospectively collected. For participants after this protocol version date, it will be collected at the time of enrollment. They will collect Gestational Age at Procedure Date (weeks/days), Cervical Preparation (Mifepristone Y/N) (Misoprostol Y/N) (Cervical Dilators Y/N, IF Y, How Many?) Genetic Indication for Termination? (Y/N).

The patients will then be given a symptom/medication log to take home. The patients will use the log to record symptoms they experience from the time they take the ondansetron or placebo to the time that they present for their procedure. The log will include the timing of the study medication, doxycycline, whether the doxycycline was taken with food (and the time of/type of food if applicable), pain medications, and misoprostol. The log will also include the time of nausea and vomiting, and the severity of the nausea and pain (if applicable).

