5.1 Safety Assessments

A comprehensive medical history will be obtained at the patient's clinic visit, and a physical exam will be performed as well to ensure that patients are not only fit and able to undergo their procedure, but also to participate in the study.

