10.2 Potential Risks

Potential risks to subjects include the possibility of an adverse reaction to ondansetron (including headache, fatigue, malaise, constipation, drowsiness, sedation, dizziness, agitation, anxiety, paresthesia, sensation of cold, pruritus, skin rash, diarrhea, urinary retention, increased serum ALT, increased serum AST, hypoxia, and fever). Important or life-threatening side effects occurring in less than 1% of patients include abdominal pain, accommodation disturbance, atrial fibrillation, depression of ST segment on ECG, dyspnea, flushing, hepatic failure (when used with other hepatotoxic medications), hiccups, hypersensitivity reaction, hypokalemia, hypotension, liver enzyme disorder, mucosal tissue reaction, myocardial infarction, neuroleptic malignant syndrome, positive lymphocyte transformation test, prolonged Q-T interval on ECG (dose dependent), second-degree atrioventricular block, serotonin syndrome, Stevens-Johnson syndrome, supraventricular tachycardia, syncope, tachycardia, tonic-clonic seizures, torsades de pointes, transient blindness (lasted ≤ 48 hours), vascular occlusive events, ventricular premature contractions, ventricular tachycardia, and weakness¹⁰. There is also a potential risk of a patient's greater realization of the nausea and vomiting they are experiencing due to doxycycline. The use of doxycycline is already standard of care.

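### Known hypersensitivity to ondansetron, the only active drug the trial adds, is not an exclusion criterion

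*Combined protocol and SAP*

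**What the plan says.** The exclusions in Section 3.2.2 cover age, English proficiency, capacity to consent, current antiemetic use, "Doxycycline allergy", hyperemesis, gastroparesis or cyclical vomiting, and inability to swallow pills. That is eight entries, one of them a drug allergy. The inclusion criteria in 3.2.1 do not mention drug reactions.

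The trial adds one active drug, a single oral 8 mg dose of ondansetron (Section 8.2). Doxycycline is background care and, according to Section 5, not a study procedure.

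On risk, Section 10.2 introduces a list with "Important or life-threatening side effects occurring in less than 1% of patients include" and includes in it "hypersensitivity reaction, hypokalemia, hypotension".

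Three other passages bear on the point:

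- Section 5.1 requires a history and physical examination "to ensure that patients are not only fit and able to undergo their procedure, but also to participate in the study".
- Section 4.2 says: "The patients will be given a written consent form to sign that will be extensively reviewed with the individual consenting them".
- Section 5 gives the next step: "Once patients are consented, they will be randomized to either the placebo or ondansetron group".

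**The concern.** Eligibility criteria should rule out people with a known contraindication to the drug that randomization may give them. Here the protocol names hypersensitivity as a risk of ondansetron but has no entry rule to match. A woman who knows she has reacted to ondansetron can meet every criterion in Section 3.2 and be assigned to it.

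What is at stake is her safety. The tablet is taken at home the night before the procedure, so a reaction would begin away from study staff. Several people may take consent, including a coordinator and a medical student (Section 4.2). A written rule would give every candidate the same check.

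The primary comparison, the power and the analysis are not in question.

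**Working it through.** The protocol gives no figure on this point to reproduce. The check is a reading of the text, followed by a rough ceiling on how many women could be affected.

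**Does any passage supply the missing rule?**

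| Section | What it does | Bars a known ondansetron reactor? |
|---|---|---|
| 3.2.2, antiemetic entry | Excludes current users | No; a past reaction is not current use |
| 3.2.2, doxycycline entry | Excludes allergy to the background antibiotic | No; different drug |
| 4.1 | Screens interested patients for eligibility | No; the stated criteria are those in 3.2 |
| 4.2 | Written consent, reviewed with the patient | No; she may decline, but no rule is stated |
| 5 | Questionnaire asks about reflux and hyperemesis | No; drug allergy is not among the listed items, and it is completed after randomization |
| 5.1 | History and examination for fitness to participate | Not by rule; no allergy or contraindication is named |
| 6 | Tells subjects not to take antiemetics | No; concerns use during the study |
| 10.3 | Protection against risks | No; names only loss of confidentiality as an additional risk |

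No passage makes such a patient ineligible.

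**How many women could be affected?** The documents do not give the share of candidates with a known ondansetron reaction. A ceiling therefore rests on two assumptions:

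- Reaction rate r: below 0.01. This is the heading figure for the Section 10.2 list, not an estimate specific to hypersensitivity.
- Share previously exposed, e: 0.1 to 1.0. The documents give no value. Section 3.1.4 says only that the drug is in common use in pregnancy.

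The planned size is 300 subjects, 150 per arm (Section 13.1), or 320 subjects, 160 per arm (Section 3.1.1). Both are carried through.

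Upper bound on known reactors = e × r × n:

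| Group | n | e = 0.1 | e = 1.0 |
|---|---|---|---|
| All enrolled | 300 | 0.1 × 0.01 × 300 = 0.30 | 1.0 × 0.01 × 300 = 3.0 |
| All enrolled | 320 | 0.1 × 0.01 × 320 = 0.32 | 1.0 × 0.01 × 320 = 3.2 |
| Ondansetron arm | 150 | 0.1 × 0.01 × 150 = 0.15 | 1.0 × 0.01 × 150 = 1.5 |
| Ondansetron arm | 160 | 0.1 × 0.01 × 160 = 0.16 | 1.0 × 0.01 × 160 = 1.6 |

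Each entry is a bound before the Section 5.1 history removes anyone. The likely number is close to zero.

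**The case against.** The strongest reply is that Section 5.1 already deals with this. It is a required check of fitness to take part, taking part means possibly swallowing ondansetron, and a woman with a known reaction to it is hardly fit to do so. Patients are also protected by knowing what is being tested. Section 2.2 says that "patients will not know if they are being given ondansetron or placebo before taking doxycycline", which hides the arm but not the possibility of ondansetron. Recruitment is by clinicians who care for these women anyway (Section 4.1), and an unblinded pharmacist is responsible for dispensing (Section 8.4).

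This stands as a reason to rate the risk low. It does not supply the criterion. Section 5.1 gives a clinician grounds to keep a patient out but does not make her ineligible, and Sections 4.1 and 8.4 describe no allergy check. Consent lets her decline, but eligibility should not rest on self-exclusion.

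Two further objections are fair. First, the doxycycline entry does not show that ondansetron was forgotten: Section 3.3 explains that these women were chosen "as they will already be taking doxycycline as the standard of care", so that entry also helps to define the population. Second, the ceiling is driven by an assumed tenfold range of prior exposure and by a bound covering a long list of effects. It shows only that the number is small, and the finding does not depend on it.

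The screening form and the consent text are not available, so what happens in practice cannot be judged.

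**Conclusion.** The point holds and is minor. The stated criteria leave a woman with a known ondansetron reaction eligible for 1:1 assignment to the drug, and no other section bars her. Confidence in that reading of the text is high.

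The practical consequence is less certain and probably very small: one 8 mg dose, a history that would usually reveal the reaction, and, under the stated assumptions, fewer than 0.15 to 1.6 known reactors in the ondansetron arm. The defect is a missing safety rule, with no bearing on the trial's inference.

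**What to change.** Add one line to Section 3.2.2: *Known hypersensitivity to ondansetron*. Ask the matching question at screening, before randomization, in all candidates not yet enrolled. Section 5 refers to participants enrolled before the current version, so recruitment had already begun and the change can protect only those still to come.

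The cost is an amendment with one exclusion line and one screening question. Section 2.2 gives about 450 surgical terminations a year. At the same ceiling with everyone previously exposed, fewer than 0.01 × 450 = 4.5 a year would be excluded. The trial's own pool is narrower, since Section 3.2.1 restricts entry to second-trimester procedures, so the true loss would be smaller still. Sample size and analysis need no change.

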3.3 Discussion of Subject Population

Pregnant women ages 18-45 years old were selected for this study, as they will already be taking doxycycline as the standard of care when they present for abortion care.

4. SUBJECT IDENTIFICATION, RECRUITMENT AND CONSENT

4.1 Method of Subject Identification and Recruitment

Patients presenting for a surgical termination of pregnancy at Women's Health Practice will be offered the opportunity to participate in the study, after they have consented for a pregnancy termination. The investigators offering participation to patients would otherwise have routine contact with these patients, as they will be caring for them regardless of whether or not they participate in the study. If a subject is interested in participating, they will then be screened to determine if they are eligible. Patients will be assigned a random number for the study that will link together their demographic questionnaire, the two visual analog scales, their study drug, and their symptom/medication log.

4.2 Process of Consent

Patients will be consented by either [name], [name], the study coordinator, [name], [name], [name], [name] or medical student [name]. The patients will be given a written consent form to sign that will be extensively reviewed with the individual consenting them. The written consents will be stored in a locked filing cabinet, and only the study coordinator, [name] or [name] will be able to access them.

5. METHODS AND STUDY PROCEDURES

Patients will be approached for participation in the randomized controlled trial after they have completed their pre-operative consultation and have already consented for pregnancy termination. Once patients are consented, they will be randomized to either the placebo or ondansetron group. The study medication will be taken 30 minutes prior to doxycycline medication the night prior to the pregnancy termination. Doxycycline prophylaxis is currently the standard of care, and is not part of the study procedure. Randomization scheme will be generated by computer generated random number blocks using a 1:1 ratio. Allocation will be done by sequentially numbered opaque sealed envelopes. The pharmacy will be compounding the study medication so that it looks exactly like the placebo tablet, in appearance, texture and smell. Once consented and randomized during their clinic visit 1-2 days before the procedure, patients will fill out a demographic questionnaire regarding their age, race, relationship status, income and education level, pregnancy history, gestational age, and symptoms of nausea and vomiting thus far in the pregnancy. This questionnaire will also include questions regarding cigarette and THC use, as well as any diagnoses of gastroesophageal reflux disease or hyperemesis gravidarum. They will then fill out a baseline visual analog scale rating their nausea, pain and anxiety, prior to leaving the office.

The study coordinator will also conduct a chart review for select information. For participants enrolled prior to this version date, it will be retrospectively collected. For participants after this protocol version date, it will be collected at the time of enrollment. They will collect Gestational Age at Procedure Date (weeks/days), Cervical Preparation (Mifepristone Y/N) (Misoprostol Y/N) (Cervical Dilators Y/N, IF Y, How Many?) Genetic Indication for Termination? (Y/N).

The patients will then be given a symptom/medication log to take home. The patients will use the log to record symptoms they experience from the time they take the ondansetron or placebo to the time that they present for their procedure. The log will include the timing of the study medication, doxycycline, whether the doxycycline was taken with food (and the time of/type of food if applicable), pain medications, and misoprostol. The log will also include the time of nausea and vomiting, and the severity of the nausea and pain (if applicable).

When patients present to the hospital for their procedure, the study coordinator, [name], [name], or [name] will give them a second visual analog scale to fill out which asks them to rate their nausea, pain and anxiety. This scale will be identical to the one they filled out at their clinic visit. This scale will be filled out prior to their procedure. When the IV is placed for their procedure, a nurse will also draw a single 7 mL tube of blood; there are no additional needle sticks for this blood draw. The blood sample will later be tested for doxycycline serum levels.

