13. DATA ANALYSIS AND MONITORING

13.1 Sample Size Determination

Based on Reeves' study as well as anecdotal data from our clinic population, we expect vomiting to occur in approximately 30% of our patients who take their doxycycline the night before their procedure. To have 80% power to detect a 50% decrease in nausea and vomiting, we will need 122 patients in each arm of the study. In order to account for subject withdrawal or non-compliance, we intend to enroll 150 patients in each arm of the study. This will be a total of 300 subjects.

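### The plan has no nausea reading at the moment of dosing and no rule separating nausea already present from nausea after doxycycline, which costs precision and interpretability for the nausea outcomes but does not bias the comparison.

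*Combined protocol and SAP*

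**What the plan says.** Section 5 defines the log window: "The patients will use the log to record symptoms they experience from the time they take the ondansetron or placebo", ending on arrival for the procedure. As described there, the log holds the times of the study tablet and of doxycycline, the times of nausea and vomiting, and nausea severity. No reading just before the tablet is mentioned.

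The pre-dose information is of two kinds. Section 2.1 describes "a baseline visual analog scale rating their nausea, pain and anxiety at their clinic appointment 1-2 days prior to their procedure", and the section 5 questionnaire asks about "symptoms of nausea and vomiting thus far in the pregnancy". The tablet is taken the night before the procedure, 30 minutes before doxycycline. The clinic rating therefore falls on the day of the tablet or the day before. The second scale is completed at the hospital, after dosing.

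Section 3.2 excludes hyperemesis, current antiemetic use, and gastroparesis or cyclical vomiting, but not ordinary pregnancy nausea.

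The primary outcome is described in more than one way. Sections 2.1 and 2.2 give nausea and vomiting together. Section 13.1 gives its control rate for vomiting ("we expect vomiting to occur in approximately 30% of our patients who take their doxycycline the night before their procedure") and its effect for both ("To have 80% power to detect a 50% decrease in nausea and vomiting"). Section 13.2 names vomiting alone. It plans chi-square tests for dichotomous outcomes and t-tests for continuous ones, and considers only demographic variables for adjustment.

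**The concern.** Every participant is pregnant, and the plan's own questionnaire anticipates nausea before enrolment. A patient who is nauseated before the tablet and still nauseated after it has nausea inside the log window, and nothing tells the analyst how to classify her.

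Two things are at stake. The first is the question itself. Sections 1.1 and 1.2 ask about nausea associated with doxycycline. Without a reading at dosing, fewer patients with nausea in the ondansetron arm could mean that doxycycline nausea was prevented, that existing nausea was relieved, or both. A null result would be equally hard to read. The second is precision. An unadjusted t-test on logged nausea severity uses no baseline, and the baseline closest to the outcome is not collected. A reading missed at dosing cannot be recovered later.

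**Working it through.** **Inputs.** Section 13.1 gives a 30% control rate (for vomiting), a halving to 15%, 80% power and 122 per arm. Alpha is not stated; two-sided 5% is assumed because it reproduces the plan's figure. The share of patients nauseated at dosing, b, and the fraction of that nausea cleared by the tablet, r, are not in the documents. They are varied below. The documents give no control rate for nausea alone under this regimen, so the vomiting rates are borrowed.

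**The plan's figure.** n = 2p̄(1 − p̄)(1.960 + 0.842)² / d², with p̄ = 0.225 and d = 0.15: 2 × 0.225 × 0.775 × 7.849 / 0.0225 = 121.7, so 122 per arm. The plan's number reproduces. The exact power of the uncorrected Pearson chi-square at 122 per arm is 81.3%.

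**Any nausea on the log.** Existing nausea counts as an event unless the tablet clears it:

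- placebo: p₁ = b + 0.30(1 − b)
- ondansetron: p₂ = b(1 − r) + 0.15(1 − b)

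For b = 10% and r = 0: p₁ = 0.10 + 0.27 = 37.0%, p₂ = 0.10 + 0.135 = 23.5%, risk ratio 0.64.

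**New-onset nausea only**, with all randomised patients in the denominator: 0.30(1 − b) v 0.15(1 − b).

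Exact power at 122 per arm:

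| b | Any nausea, r = 0 | Any nausea, r = 0.5 | New-onset only |
|---|---|---|---|
| 10% | 37.0% v 23.5%: 64% | 37.0% v 18.5%: 91% | 27.0% v 13.5%: 76% |
| 20% | 44.0% v 32.0%: 50% | 44.0% v 22.0%: 96% | 24.0% v 12.0%: 70% |
| 30% | 51.0% v 40.5%: 37% | 51.0% v 25.5%: 99% | 21.0% v 10.5%: 63% |

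The risk ratio with r = 0 is 0.64, 0.73 or 0.79; with r = 0.5 it is 0.50 throughout.

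**Where the ranking turns.** New-onset nausea has more power than any nausea when nothing responds, and less once roughly 15–20% of existing nausea responds. At b = 10%, r = 0.20, any nausea gives 77% against 76%. At b = 30%, r = 0.15, it gives 65% against 63%.

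**Vomiting alone as primary.** Nausea at dosing adds no vomiting events, so the plan's power is unchanged at 81%.

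**Nausea severity.** Adjusting for a baseline that correlates ρ with the outcome multiplies the residual variance by 1 − ρ². That is 0.91 at ρ = 0.3 and 0.64 at ρ = 0.6. Both correlations are assumptions, chosen to show the scale of the gain if a reading at dosing tracks the outcome more closely than the clinic rating does.

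**The case against.** The strongest reply is that the plan never says nausea present at dosing counts as an event. Section 2.1 places the outcome after both the study drug and doxycycline, which points away from counting earlier symptoms. The log also records clock times, so nausea entered at tablet time is dated before doxycycline. Both points stand in part. The gap is a missing definition, not a stated rule to count such nausea. The times help, but a log that opens at the tablet does not reliably identify nausea that began earlier and was entered later.

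A reader might infer that existing nausea necessarily dilutes the effect and that the loss of power is large. The documents do not support that. It requires existing nausea not to respond to an antiemetic, and the table shows power rising if half of it does. For the same reason the documents do not support replacing any nausea with new-onset nausea.

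A reader might also infer that the primary analysis is compromised. Under section 13.2 it is not, because vomiting alone is primary there.

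Nor is the clinic rating always remote: for a visit the day before the procedure, it is taken on the day of the tablet. The exclusions in section 3.2 reduce nausea at dosing further, though they do not rule it out.

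Finally, section 5 refers to participants enrolled before the current version, so a new log line comes too late for some of them. That limits the remedy but does not remove the reason for it.

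**Conclusion.** The concern holds for the nausea outcomes, as a matter of precision and interpretation. It is not a bias: randomisation should balance nausea at dosing between the arms. It bears on the primary outcome only if sections 2.1, 2.2 and 13.1 prevail over section 13.2, and those sections must be reconciled in any case.

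The direction of the effect on power for any nausea is undetermined. At 122 per arm it ranges from 37% (30% nauseated at dosing, none responding) to 99% (30% nauseated, half responding), against 81% with nobody nauseated at dosing. This range rests on borrowed vomiting rates, an assumed two-sided 5% test, and an assumed prevalence and response.

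Two conclusions do not depend on those assumptions. The plan as written has no dependable way to tell prevention from relief. And section 13.2 makes no use of baseline nausea when comparing nausea severity.

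**What to change.** 1. Add one line at the top of the take-home log, completed immediately before the study tablet: nausea severity on the log's own scale, and vomiting since leaving clinic (yes/no).
2. In section 13.2, replace the unadjusted t-test for nausea severity with an analysis of covariance. Use the pre-tablet reading as baseline, or the clinic visual analog scale where that reading is missing, including for everyone enrolled before the change. If the two scales differ, add an indicator for which one was used.
3. Keep all randomised patients and keep any nausea as an outcome. Define new or worsened nausea relative to the pre-tablet reading, and report it beside any nausea as a supporting outcome.
4. Reconcile the primary outcome across sections 2.1, 2.2, 13.1 and 13.2.

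The cost is one line on an existing form, a few sentences in section 13.2 and the reconciling edits. The downside is incomplete data: the pre-tablet reading will be missing for participants already enrolled and for some later ones who leave it blank. For them the clinic scale serves as the covariate, and new or worsened nausea will be less well determined.
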